# 6 STUDY PERIODS, TREATMENT REGIMENS AND POPULATIONS FOR ANALYSES

# 6.1 Study Periods

- Baseline period:
  - Baseline evaluations or events will be defined as evaluations or events that occur before
    the date and time of the first dose of study treatment. Evaluations (laboratory tests, pulse
    and vital signs) on the same date and time of the first dose of study treatment will be

- considered as baseline evaluations. Events (AEs) on the same date and time of the first dose of study treatment will not be considered as pre-treatment events.
- In cases where the time (onset time of event or evaluation time and dosing time) is missing or not collected, the following definitions will apply:
  - Pre-treatment AEs will be defined as AEs with an onset date prior to but not including the day of the first dose of study treatment;
  - ♦ Baseline evaluations (laboratory tests, pulse oximetry and vital signs) will be defined as evaluations with a date on or prior to the day of first dose of study treatment.
- If there are multiple valid assessments on or prior to the first dose of study treatment:
  - For laboratory tests, the latest non missing labs value on or before first dose date (and time if collected) will be used as the baseline in the analyses. For 'LIPASE' and 'GLUCOSE', for treated subjects only, the last predose assessment with non-missing toxicity grade will be considered as baseline. If multiple assessments exist with the same collection date (and time if collected) and entry date and time, then the first observation is used as baseline.
  - ♦ For Eastern Cooperative Oncology Group (ECOG) performance status (PS), the latest ECOG PS value prior to or on the first dose date (and time if collected) will be used as the baseline in the analyses. If multiple records fall on the last date then the record with the highest value of ECOG PS will be considered as baseline.
  - For PD-L1, among the records prior to or on first dose date (and time if collected), identify first those with quantifiable test result. If there are no records with quantifiable test result, then select those with indeterminant result ("INDETERMINATE"). If there are no records with indeterminant test result, then select those with unavailable result ("NOT EVALUABLE). If there are no records with unavailable test result, then select those with not reported or not available result (all other records). The latest record will be used as the baseline in the analyses. If there is more than one record for the latest date, then choose the one with the greatest specimen ID.
  - ♦ For Anti-Drug Antibody (ADA), the record related to the most recent assessment among those records where date (and time if collected) of nivolumab/ipilimumab immunoglobulin (IMG) assessment is less than or equal to the date (and time if collected) of the first nivolumab/ipilimumab dose date.

#### • Post baseline period:

- On-treatment AEs will be defined as AEs with an onset date and time on or after the date and time of the first dose of study treatment (or with an onset date on or after the day of first dose of study treatment if time is not collected or is missing). For subjects who are off study treatment, AEs will be included if event occurred within a safety window of 100 days after the last dose of study treatment. No "subtracting rule" will be applied when an AE occurs both pre-treatment and post-treatment with the same preferred term and grade.
- On-treatment evaluations (laboratory tests, pulse oximetry and vital signs) will be defined as evaluations taken after the day (and time, if collected and not missing) of first dose of study treatment. For subjects who are off study treatment, evaluations should be within a safety window of 100 days after the last dose of study treatment.

 Late-emergent drug-related AEs will be defined as drug-related AEs with an onset date greater than 100 days after the last dose of study treatment in subjects who are off study treatment.

# 6.2 Treatment Regimens

Treatment group "as randomized" corresponds to the treatment group assigned by the Interactive Response Technology (IRT) system.

- Arm A: Nivolumab 3 mg/kg IV every 2 weeks + Ipilimumab 1 mg/kg IV every 6 weeks until progression, unacceptable toxicity, or a maximum of 24 months from first study treatment.
- Arm B: Cetuximab 400 mg/m² IV for the initial dose only, then 250 mg/m² weekly + cisplatin (100 mg/m²) or carboplatin (AUC of 5 mg per milliliter per minute) on Day 1 and fluorouracil (1000 mg/m² per day for 4 days) every 3 weeks for maximum of 6 cycles followed by maintenance cetuximab at 250 mg/m² weekly (or every 2 weeks, per local prescribing information) until disease progression or unacceptable toxicity; the choice of cisplatin or carboplatin is at the discretion of the investigator.

The treatment group "as treated" will be same as the treatment group "as randomized" by IRT unless a subject received the incorrect study treatment for the entire period of treatment, in which case the subject's treatment group "as treated" will be defined as the incorrect study treatment.

Unless otherwise specified, the safety analysis will be based on the treatment group "as treated".

Unless otherwise specified, the efficacy analysis will be based on the treatment group "as randomized".

# 6.3 Populations for Analyses

- All Enrolled Subjects: All subjects who signed an informed consent form and were registered into the IVRS.
- All Randomized Subjects: All enrolled subjects who were randomized to either treatment arm.
- All Randomized PD-L1 CPS  $\geq$  20 Subjects: All randomized subjects with PD-L1 CPS  $\geq$  20
- All Randomized PD-L1 CPS  $\geq$  1 Subjects: All randomized subjects with PD-L1 CPS  $\geq$  1.
- All Randomized Tumor PD-L1 expression < 1% Subjects: All randomized subjects with Tumor PD-L1 expression < 1%
- All Randomized PD-L1 CPS < 20 Subjects: All randomized subjects with PD-L1 CPS < 20
- All Randomized GEP  $\geq$  10 Subjects: All randomized subjects with GEP  $\geq$  10.
- All Randomized TMB  $\geq$  7 Subjects: All randomized subjects with TMB  $\geq$  7.
- All Treated Subjects: All subjects who received at least one dose of nivolumab, ipilimumab, cetuximab, cisplatin, carboplatin or 5-FU.
- Treated Subjects with PD-L1 CPS ≥ 20: All subjects who received at least one dose of nivolumab, ipilimumab, cetuximab, cisplatin, carboplatin or 5-FU and have PD-L1 CPS ≥ 20 at baseline.
- All PK Subjects: All subjects with available serum time-concentration data
- Immunogenicity Evaluable Subjects:

- Nivolumab ADA Evaluable Subjects: all treated subjects with baseline and at least
   1 post-baseline pre-infusion nivolumab immunogenicity assessment.
- Ipilimumab ADA Evaluable Subjects: all treated subjects with baseline and at least
   1 post-baseline pre-infusion ipilimumab immunogenicity assessment.
- All PD-L1 CPS Tested subjects: All subjects, randomized or not, who had a tumor biopsy specimen available for tumor cell expression testing. This includes both randomized and screen failure subjects.

Key analyses of study conduct, demographics, and efficacy will be done on the all randomized population and repeated on the randomized PD-L1 CPS  $\geq$  20 population. Subjects in these analyses will be grouped as assigned at randomization.

Key analyses of exposure and safety will be done on the all treated population and repeated on the treated PD-L1 CPS  $\geq$  20 population. Subjects in these analyses will be grouped by treatment received rather than treatment assigned at randomization. Treatment arm received will be equal to treatment arm as randomized, unless the subject received the non-assigned regimen for all doses.

#### 7 STATISTICAL ANALYSES

#### 7.1 General Methods

Unless otherwise noted, discrete variables will be tabulated by the frequency and proportion of subjects falling into each category, grouped by treatment. Percentages given in these tables will be rounded to the first decimal and, therefore, may not always sum to 100%. Percentages less than 0.1 will be indicated as '< 0.1'. Continuous variables will be summarized by treatment group using the mean, standard deviation, median, minimum, and maximum values.

Time-to-event variables (e.g. time-to resolution) will be analyzed using the Kaplan-Meier technique. When specified, the median will be reported along with 95% CI using Brookmeyer and Crowley method (using log-log transformation for constructing the confidence intervals).

The conventions to be used for imputing missing and partial dates for analyses requiring dates are described in Section 8.

# 7.1.1 Adverse Events, Serious Adverse Events, Multiple Events, Select Adverse Events, Other Events of Special Interest and Immune-Mediated Adverse Events

Drug-related AEs are those events with relationship to study drug "Related", as recorded on the CRF. If the relationship to study drug is missing, the AE will be considered as drug-related.

Serious adverse events consist of AEs deemed serious by the Investigator and flagged accordingly in the CRF and clinical database.

Adverse events leading to study drug discontinuation are AEs with action taken regarding study drug(s) = "Drug was discontinued".

Adverse events leading to dose delay are AEs with action taken regarding study drug(s) = "Drug was delayed".

Adverse events leading to dose reduction are AEs with action taken regarding study drug(s) = "Dose was reduced".

Adverse events will be coded using the Medical Dictionary for Regulatory Activities (MedDRA), and the most recent version of the dictionary at the time of the database lock will be used. Adverse events results will be graded for severity using NCI Common Terminology Criteria for Adverse Events (CTCAE) and the most recent version of the criteria at the time of the database lock will be used.

In the AE summary tables, unless otherwise specified, subjects will be counted only once at the Preferred Term (PT), only once at the System Organ Class (SOC), and only once at subject level for the counting of total number of subjects with an AE. The AE tables will be sorted by the SOCs and then PTs. SOC will be ordered by descending frequency overall and then alphabetically. PTs will be ordered within SOC by descending frequency overall and then alphabetically. The sorting will be done based on the 'Any Grade' column of the experimental arm when arms are presented side-by-side.

Unless otherwise specified, the AE summary tables will be restricted to on-treatment events regardless of the causality.

Analyses that take into account the multiple occurrences of a given adverse event will be conducted (see Section 7.6.9). To prepare these analyses, the CRF data will be processed according to standard BMS algorithms  in order to collapse adverse event records into unique records based on the preferred term. These data will be presented as the rate per 100 person-years of exposure. These analyses will take into account all on-treatment events (allowing more than 1 event per subject) and the total exposure time. The person-year exposure will be computed as the sum over the subjects' exposure expressed in years where the exposure time is defined as

- (Date of last dose of study treatment date of first dose of study treatment + 101 days )/365.25, for subject who are off study treatment and were followed for at least 30 days (or 100 days, depending on the analysis) after last dose of study treatment.
- (Last known alive date date of first dose of study treatment +1)/365.25, for subjects who are still on-treatment or who are off study treatment and were followed less than 100 days after last dose of study treatment.

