# 7.6.9 Multiple Events

The following summary tables will be provided:

- A table showing the total number and rate (exposure adjusted) of occurrences for all AEs.
- A table showing the total number and rate (exposure adjusted) of occurrences for AEs occurring in at least 5% of subjects in any treatment group.

In addition, the rate (exposure adjusted) and its 95% CI evaluated for different time intervals will be displayed graphically for each treatment group. This analysis will be limited to the rate of all AEs and all drug-related AEs. The analyses will be conducted using the 30-day safety window.

A listing displaying the unique instances of all AEs, i.e., after duplicates have been eliminated and overlapping and contiguous occurrences of the same event (i.e. same PT) have been collapsed will be provided. No formal comparisons will be made between treatment groups.

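### The 30-day exposure-adjusted AE rates in SAP 7.6.9 rest on person-time built for a 100-day window, and subjects followed 30 to 99 days meet both exposure rules

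*SAP*

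**What the plan says.** SAP 7.1.1 expresses multiple-event AE data as events per 100 person-years and gives two exposure rules.

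- **Bullet 1** takes last dose date minus first dose date, with the ending "date of first dose of study treatment + 101 days )/365.25". It applies to subjects off treatment who "were followed for at least 30 days (or 100 days, depending on the analysis) after last dose of study treatment".
- **Bullet 2** runs from first dose to last known alive date, plus 1 day. It applies to subjects still on treatment or "off study treatment and were followed less than 100 days after last dose of study treatment".

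SAP 7.6.9 lists the outputs that use this exposure: a rate table for all AEs, a rate table for AEs in at least 5% of subjects in any arm, and a graph of the rate and its 95% CI "evaluated for different time intervals will be displayed graphically for each treatment group". The paragraph on the graph ends with "The analyses will be conducted using the 30-day safety window". The section closes by saying "No formal comparisons will be made between treatment groups".

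For subjects off treatment, the general definition of on-treatment events in SAP 6.1 is longer: "AEs will be included if event occurred within a safety window of 100 days after the last dose of study treatment".

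**The concern.** In bullet 1 the follow-up condition changes with the analysis but the offset does not. In bullet 2 the cut-off is fixed at 100 days. The rules therefore work for a 100-day analysis and fail for a 30-day one in two ways.

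1. The denominator runs up to 70 days past the last day on which an event can enter the numerator, so the rate is too low.
2. A subject followed 30 to 99 days after last dose meets both bullets, and no precedence is stated. Two programmers could derive different denominators from the same text. If follow-up ended in death, bullet 1 counts time after death.

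The rates are shown by arm, and the shortfall depends on time on treatment. SAP 2.1 gives the arms different stopping rules: a 24-month maximum in Arm A, and up to six chemotherapy cycles followed by cetuximab until progression or toxicity in Arm B. Durations may therefore differ, so the bias need not cancel. Understating AE rates is also the non-conservative direction for a safety summary.

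**Working it through.** **Inputs.** The offset (+101), the follow-up conditions (30 or 100 days in bullet 1, below 100 in bullet 2) and the 30-day window come from SAP 7.1.1 and 7.6.9. The documents give no treatment durations, so every duration below is an assumption. D is days from first to last dose (or its mean), and F is days of follow-up after last dose.

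**Offset.** An inclusive count to last dose + W days adds W + 1. W = 100 gives 101, which reproduces the SAP figure. W = 30 gives 31, which appears nowhere. The difference is 70 days per subject.

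**Whole-exposure rate, all subjects off treatment with F ≥ 100.** Written rate / window-matched rate = (D + 31)/(D + 101). The understatement is 70/(D + 101).

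| Mean D (days) | Ratio | Understatement |
|---|---|---|
| 0 | 31/101 = 0.307 | 69% |
| 90 | 121/191 = 0.634 | 37% |
| 150 | 181/251 = 0.721 | 28% |
| 179 | 210/280 = 0.750 | 25% |
| 365 | 396/466 = 0.850 | 15% |
| 730 | 761/831 = 0.916 | 8% |

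These are upper limits. They shrink when subjects die or are censored before day 100, provided bullet 2 is used for them, or remain on treatment. For example, assume exponential survival after last dose with a median of 183 days, and bullet 2 below 100 days. The hazard is ln 2/183 = 0.003788 per day. Mean follow-up truncated at 30 days is (1 − e^(−0.1136))/0.003788 = 28.4 days, and truncated at 100 days it is 83.2 days. At D = 90 the understatement becomes 1 − (91 + 28.4)/(91 + 83.2) = 31.5%. At D = 150 it is 1 − (151 + 28.4)/(151 + 83.2) = 23.4%.

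**Subjects meeting both bullets (30 ≤ F ≤ 99) in a 30-day analysis.** Bullet 1 gives D + 101, bullet 2 gives D + F + 1, and the 30-day window needs D + 31.

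| D, F | Bullet 1 | Bullet 2 | Needed | Understatement, bullet 1 / bullet 2 |
|---|---|---|---|---|
| 90, 40 | 191 | 131 | 121 | 36.6% / 7.6% |
| 90, 60 | 191 | 151 | 121 | 36.6% / 19.9% |
| 150, 60 | 251 | 211 | 181 | 27.9% / 14.2% |

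At F = 29 only bullet 2 applies, and at F = 100 only bullet 1, so the overlap is exactly 30 to 99 days.

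**Rate-by-interval graph.** The intervals are assumed to be days 0–91 and 91–183, with exponential D capped at 730 days. The understatement is 1 − (person-days to D + 31)/(person-days to D + 101) within each interval. The first two result columns assume F ≥ 100 for everyone. The last two use the 183-day median survival above, with bullet 2 below 100 days.

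| Mean D after cap | Days 0–91 | Days 91–183 | Days 0–91, with deaths | Days 91–183, with deaths |
|---|---|---|---|---|
| 90 | 18% | 54% | 15% | 48% |
| 149 | 12% | 37% | 10% | 32% |
| 228 | 8% | 25% | 6% | 21% |

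Check on the first cell: person-days to D + 31 are 31 + 90(1 − e^(−60/90)) = 74.8, person-days to D + 101 are 91, and 1 − 74.8/91 = 18%. The error grows in the later interval, so the shape of the curve is distorted as well as its level.

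**Between arms, equal true rates, F ≥ 100.** Mean D of 90 versus 150 days gives 0.634/0.721 = 0.88. Mean D of 90 versus 120 days gives 0.634/0.683 = 0.93, where 0.683 = 151/221. Which arm is shorter is not known.

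**The case against.** The best counter-argument concerns scope. In 7.6.9 the tables come first and the 30-day sentence closes a separate paragraph about the graph. Section 7.1.1 says these analyses take all on-treatment events, and SAP 6.1 gives on-treatment AEs a 100-day window. On that reading the tables count events to day 100, +101 is right for them, and the bullets do not overlap.

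This reading is possible but not settled. The graph is described in the singular, while the window sentence refers to analyses in the plural, which fits the whole section better. The on-treatment default does not decide it either: 7.1.1 restricts AE summary tables in general to on-treatment events, yet 7.6.5 runs most of its tables on a 30-day window. Sections 7.6.5, 7.6.7 and 7.6.8 name their windows outright, whereas on the narrow reading 7.6.9 leaves the tables' window to inference. On either reading the graph is a 30-day analysis with a 100-day denominator.

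It can also be said that the wording about the analysis shows two variants were intended and a programmer would supply +31. That may be so, but +31 is not in the plan, and the bullet 2 cut-off would still conflict.

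Two further points stand. The whole-exposure percentages are upper limits and apply to the tables only if those are 30-day analyses. The outputs are descriptive, with no bearing on alpha, OS or stopping.

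**Conclusion.** The concern holds. As written, the exposure rule is wrong for any 30-day analysis. That is certain for the rate-by-interval graph and likely for the two tables. The direction is always toward lower AE rates.

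For mean durations between 90 and 365 days, the whole-exposure understatement runs from 37% down to 15% when everyone is off treatment and followed at least 100 days. The assumed post-treatment mortality lowers the 90-day figure to about 31.5%. All sizes rest on assumed durations and follow-up, and the size and direction of any between-arm distortion cannot be determined from the documents. Because the consequence is confined to descriptive by-arm safety rates, this is a correction that should be made, not one that threatens the trial's conclusions.

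**What to change.** In SAP 7.1.1, tie both the offset and the cut-off to the window:

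- **30-day analyses:** (last dose date − first dose date + 31)/365.25 for subjects off treatment and followed at least 30 days after last dose; (last known alive date − first dose date + 1)/365.25 for subjects still on treatment or followed less than 30 days.
- **100-day analyses:** keep +101 with the 100-day cut-off in both bullets.

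In SAP 7.6.9, state which window the two rate tables use.

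The cost is two lines in 7.1.1, one sentence in 7.6.9 and one programming parameter, with no new data. Reported 30-day rates will be higher. If the tables are declared 100-day analyses, only the graph changes.

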## 7.1.1.1 Select Adverse Events (EU Submission)

The select Adverse Events (select AEs) consist of a list of preferred terms grouped by specific category (e.g. pulmonary events, gastrointestinal events categories, etc.). AEs that may differ from or be more severe than AEs caused by non-immunotherapies and AEs whose early recognition and management may mitigate severe toxicity are included as select AEs. Categories of select AEs may include subcategories (e.g. adrenal disorders, diabetes, pituitary disorders, and thyroid disorders are subcategories of the endocrine event category).

The list of MedDRA preferred terms used to identify select adverse events is revisited quarterly and updated accordingly. The preferred terms used for the selection at the time of the database lock will be provided by categories/subcategories.

In addition to the frequency and worst severity of select AEs, time-to onset, time-to resolution, and time-to resolution where immune modulating medication was initiated will be analyzed for each specific category/subcategory of drug-related select AEs when applicable.

Further details on the definitions of select adverse event, time-to onset and time-to resolution are described in APPENDIX 1.

# 7.1.1.2 Other Events of Special Interest

Other events of special interest (OEOSI) consist of a list of preferred terms grouped by specific category. The list of MedDRA preferred terms used to identify OEOSI is revisited quarterly and updated accordingly. The preferred terms used for the selection at the time of the database lock by categories will be provided.

# 7.1.1.3 Immune-Mediated Adverse Events (US Submission)

In order to further characterize AEs of special clinical interest, analysis of immune-mediated AEs (IMAE) will be conducted. IMAEs are specific events (or groups of PTs describing specific events) that include pneumonitis, diarrhea/colitis, hepatitis, nephritis/renal dysfunction, rash, endocrine (adrenal insufficiency, hypothyroidism/thyroiditis, hyperthyroidism, diabetes mellitus, and hypophysitis), and other specific events, considered as potential immune-mediated events by investigator that meet the definition summarized below:

- those occurring within 100 days of the last dose,
- regardless of causality,
- treated with immune-modulating medication (of note, endocrine AEs such as adrenal insufficiency, hypothyroidism/thyroiditis, hyperthyroidism, diabetes mellitus, and hypophysitis are considered IMAEs regardless of immune-modulating medication use, since endocrine drug reactions are often managed without immune-modulating medication).
- with no clear alternate etiology based on investigator assessment, or with an immune-mediated component

The list of MedDRA preferred terms used to identify IMAEs is revisited quarterly and updated accordingly. The preferred terms used for the selection at the time of the database lock by categories will be provided.

#### 7.1.2 Laboratory Tests

Clinical laboratory parameters (hematology, serum chemistry and electrolytes) will be evaluated.

Laboratory tests will be graded using the NCI Common Terminology Criteria, and the most recent version of the criteria at the time of the database lock will be used.

Clinical laboratory data will be first analyzed using International System of Units (SI). Analyses will be repeated using US conventional units.

In the laboratory summary tables, unless otherwise specified, subjects will be counted only once for each lab parameter according to their worst on treatment CTC grade (worst being the highest CTC grade). The laboratory tables and listings will be sorted by laboratory category, laboratory subcategory and laboratory test code sequence number.

